5.2 Safety	21
5.3. Other variables	21
5.4 Appropriateness of measurements	21
6 Investigational plan	22
6.1 Visit schedule	22
6.2. Patient recruitment process	22
6.3 Details of trial procedures	22
6.3.1 Baseline clinic visit (start of study)	22
6.3.2 Haemodialysis visits during study observation period	24
6.3.3 Week 1 and Week 2 clinic visits	24
6.3.4 Week 3 visit (end of study observation period)	24
7. Statistical methods and determination of sample size	25

7.1	Statistical design and model	25
7.2	Null and alternative hypotheses	25
7.3	Planned analyses	25
7.3.1	Primary analyses	26
7.3.2	Secondary analyses	26
7.3.3	Safety analyses	26
7.3.4	Interim analyses	26
7.3.5	Health economic analyses	26
7.4	Handling of missing data	26
7.5.	Randomisation	26
7.6	Determination of sample size	26
8.	Informed consent, data protection and trial records	27
8.1	Study approval, patient information and informed consent	27
8.2	Data quality assurance	27
8.3	Records	27
8.3.1	Source documents	27
8.3.2	Direct access to source data and documents	27
8.3.3	Storage of records	27
8.4	Statement of confidentiality	28
8.5	Completion of trial	28
8.6	Protocol violations	28
8.7	Compensation available to the patient in the event of study-related injury	28
9	References	28
10.	Appendices	29
Appendix 10.1	Cointerventions protocol	29
Appendix 10.2	Recruitment of patients	29
Appendix 10.3	Training of personnel	29
Appendix 10.4	Trial registration on public registry	30
Appendix 10.5	Funding	30
Appendix 10.6	Incentives for participation:	30

Signatures

31

PROTOCOL SUMMARY

PRODUCT	Sixty wearable hydration monitor
CLINICALTRIALS.GOV IDENTIFIER	NCT 00000000
PROTOCOL TITLE	Pilot-scale, single-arm, observational study to assess the utility and acceptability of a wearable hydration monitor in haemodialysis patients
COORDINATING INVESTIGATOR	[name], Beaumont Hospital, [name]
NUMBER OF TRIAL SITES	One: Beaumont Hospital dialysis centre.
STUDY OBJECTIVES	To determine the validity and reproducibility of the fluid status data captured by a wearable hydration monitor (Sixty device) compared with bioimpedance and haemodialysis machine data) in ambulatory haemodialysis patients. To assess the utility and patient acceptability of the Sixty device.
METHODOLOGY	Open, prospective, single-arm observation. Observation period: 3 weeks.
NUMBER OF SUBJECTS	Total randomised: 20
DIAGNOSIS	End Stage Kidney Disease requiring regular ongoing haemodialysis
MAIN CRITERIA FOR INCLUSION	Age ≥ 18 years, demonstrated understanding of use of the Sixty device and home blood pressure monitor, written informed consent
TEST PRODUCT	Sixty wearable hydration monitor
COMPARATOR PRODUCT	None
END OF STUDY DEFINITION	3 weeks
PRIMARY ENDPOINT	Volume status measured by Sixty device compared to haemodialysis machine and bioimpedance data
SECONDARY ENDPOINTS	Acceptability of Sixty device
INTERIM ANALYSIS	None planned
STATISTICAL METHODS	Descriptive tables or figures will be prepared. Within-patient comparison of fluid status data as determined by different methodologies.

FLOW CHARTS

Flow chart 1 Assessments during observation period

	study observation period (3 weeks)				
	Baseline clinic visit	At each dialysis session	Week 1	Week 2	Week 3 (end)
Informed consent	X				
Demographic data (include dialysis & medicines history)	X				
Vital signs, body weight, routine hemodialysis measurements in-clinic ^A	X	X	X	X	X
Assess fluid status with bioimpedance ^B	X		X	X	X
Instruction/patient training on use of Sixty device	X				
Wear Sixty device daily ^C	X	X	X	X	X
Download data and recharge Sixty device ^D		X	X	X	X
Record symptoms related to fluid status ^E	X	X	X	X	X
Record adverse events ^F	X	X	X	X	X
Patient records blood pressure at home once/day ^G	once/day throughout study				
Stop using Sixty device ^H					X
Acceptability of Sixty device questionnaire ^I					X
End of study					X

^A Routine measurements (at each hemodialysis session) include total fluid removal, interdialytic weight gain (IDWG), proportion of haemodialysis sessions in which IDWG is $\leq 4\%$, pre-dialysis and post-dialysis weight, pre-dialysis, intradialytic and post dialysis BP and pulse rate.

^B Fluid status will be assessed by bioimpedance measurements immediately before start and immediately after end of haemodialysis.

^C Sixty is a wrist-worn hydration monitor. It uses optical spectroscopy and machine learning algorithms to determine hydration level. No data is displayed to the patient. The device should first be worn by the patient for five minutes before the haemodialysis session at the Baseline Visit and throughout that haemodialysis session. It should then be worn throughout the study observation period, including during all haemodialysis sessions.

1.1 Medical background

End stage kidney disease is defined by kidney failure severe enough to require some form of renal replacement therapy. This replacement has three forms, kidney transplant, haemodialysis and peritoneal dialysis.

Haemodialysis is the most common form of replacement therapy and usually entails three sessions of dialysis per week on alternate days starting either on Monday or Tuesday. The period between dialysis sessions is known as the interdialytic period and as dialysis is delivered on alternate days there is one interdialytic period per week that is longer than the other. In order to maintain extracellular fluid balance and to prevent high blood pressure, haemodialysis sessions focus on removing the fluid that was gained between dialysis sessions.

Haemodialysis patients experience high rates of mortality, driven largely by an exceptionally high rate of cardiovascular (CV)-related mortality, which exceeds that of the general population by 10-to 20-fold^{1,2}. High levels of both interdialytic weight gain and rate of fluid removal during dialysis have been linked with increased mortality, particularly during the longer interdialytic period¹. It is postulated that the haemodynamic effects of high fluid removal rates during dialysis may result in cardiovascular morbidity and mortality. Similarly, volume depletion induced by excessive ultrafiltration is associated with myocardial stunning, cerebrovascular events and mortality^{3,4}.

In one study⁵ up to 27% of prevalent dialysis patients were estimated to be volume overloaded. The prevalence increased to 66.2% when patients with mild fluid overload are included. 31.1% of patients met the criteria for normovolaemia and 2.7% were classified as fluid-depleted.

Technology to evaluate the optimal volume status of haemodialysis exists. Use of validated measures of volume such as bioimpedance, however, are limited by time and cost constraints⁶. Volume reduction as guided by alternative interventions, such as blood volume monitoring (BVM) have been associated with increased mortality⁷.

[figure not shown]
Wearable technology which can record patient parameters such as vital signs, electrical rhythms, and serum potassium levels have allowed patients to monitor their conditions in real-time. A similar option for volume monitoring in haemodialysis patients would enable patients and care providers to optimise fluid status and reduce complications associated with under- and overhydration. To date, no specific wearable hydration monitor for haemodialysis patients is available and validated. The purpose of this trial is to compare a wearable hydration monitor against gold standard measurements of volume in haemodialysis patients.

To date, this approach has not been explored in haemodialysis patients.

1.2 Product profile

The Sixty device is a wearable hydration monitor that is currently in development. Photographs of the current prototype and expected final designs are shown in Figure 1.2: 1.

Figure 1.2: 1: Photographs of prototype and expected final design of Sixty device

The prototype device (left-hand image) measures 66mm x 48mm x 10mm. The on/off button and charging port are visible on the top edge. The surface facing the camera will be in contact with the dorsal surface of the user's wrist. The expected final design is shown in the right-hand image. This is expected to be approximately the size of a commercially available smart watch (e.g. Apple watch).

The Sixty device uses diffuse reflectance spectroscopy to measure fluid levels subdermis. Optical sensors shine light of a specific wavelength onto the skin and the amount of light reflected back can be correlated to different body components (e.g. water). The machine learning algorithm is trained using a calibrated data set of known fluid states allowing the device to interpret the data and provide feedback on fluid status.

The prototype device used in this study does not reflect the final aesthetic or "looks like" design, but provides the necessary functionality to establish proof of principle in fluid overloaded patients. It is designed to be very simple to operate, with only one button to turn it on and off. The simple user interface indicates that the device is on/off and is functioning correctly. The prototype device will only collect data and does not provide feedback to the user on their hydration status. Data is collected locally on a memory card (i.e. SD card) which will be removed periodically to recover the data.

The device and battery is designed to run for an extended period and can be charged via a USB cable. Charging the device and collection of data will be coordinated at the haemodialysis study centre to minimise data gaps and to reduce unnecessary complexity for the patient.

Patent acceptability will be assessed.

2. Rationale, objectives and benefit-risk assessment

2.1 Rationale for performing the trial

This trial will evaluate if a wearable hydration monitor (the Sixty device), has validity and reproducibility against gold standard measurements of fluid volume in haemodialysis patients.

This is a pilot-scale study to assess if this approach has merit and could be tested and developed further.

As no specific wearable hydration monitor for haemodialysis patients is available and validated, there is sufficient justification in testing the effectiveness and acceptability of the Sixty device in a controlled observational setting.

2.2 Trial objectives

The objective of this pilot-scale study is to assess how the Sixty hydration monitoring device functions when used in a range of haemodialysis patients of varying age, gender, body habitus and volume status. Patients with a range of baseline fluid status (ranging from 15% above to 10% below their dry weight as determined by bioimpedance) will be considered for enrollment.

The primary objective is to determine the validity and reproducibility of the data captured by the Sixty device in haemodialysis patients. (The goal is to determine if the data captured by the Sixty device and the additional haemodialysis parameters described can be developed into algorithms that provide actionable insights to better manage fluid overload in the interdialytic period.)

Haemodialysis parameters will be assessed as usual during the study and will include:

- total fluid removal (each haemodialysis session)
- interdialytic weight gain (IDWG)
- proportion of haemodialysis sessions in which IDWG is $\leq 4\%$.
- pre-dialysis weight
- post-dialysis weight
- pre-dialysis blood pressure (BP)
- intradialytic BP

- post-dialysis BP
- number and type(s) of BP medications
- requirement for nursing interventions (e.g. stopping dialysis or administering fluid bolus)
- adverse events requiring or prolonging hospitalisation
- requirement for additional unscheduled dialysis

Fluid volume data measured by the Sixty device will be compared to recorded extracted fluid and volume status as measured by haemodialysis machine data and bioimpedance findings.

Patient-reported symptoms related to haemodialysis and the underlying medical condition will be recorded before haemodialysis. Symptoms data will be assessed and compared with fluid status data.

Data on BP measured once/day at home during the interdialytic period will also be recorded.

An additional objective of this observational study is to assess the acceptability and utility of the Sixty device (from the patient perspective).

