3.2 Discussion of trial design, including choice of control group

This is a pilot-scale, prospective, open-label, single-arm observational study.

All patients will be allocated to the same observation sequence.

Patients will follow their usual haemodialysis regimen throughout the study. Patients' dry weight will be optimised using gold standard care (bioimpedance measurements) during the study.

Clinical assessments (e.g. IDWG, BP, pulse rate, ultrafiltration volume, symptoms) will be assessed at each dialysis visit.

The trial design will allow assessment of the validity and reproducibility of data collected by the Sixty device in haemodialysis patients. Data from the Sixty device will be compared against other validated methods of volume assessment (haemodialysis machine and bioimpedance data) and with observed symptoms in patients across a range of age, genders and volume status.

The study will also allow evaluation of the utility and acceptability of the Sixty device in a haemodialysis patient population. This will be assessed from the patient perspective.

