5.1 Efficacy

5.1.1 Efficacy endpoints

5.1.1.1 Primary endpoint

The primary endpoint will be to evaluate the accuracy of the Sixty device data in assessing volume in haemodialysis patients compared to gold standard monitoring techniques. The volume status as measured by the Sixty device will be compared with volume status as measured by bioimpedance, patient symptoms, and traditional haemodialysis parameters.

The primary endpoint variables include:

Comparison of volume status as measured by Sixty device compared to bioimpedance pre- and post-dialysis:

- volume overload as defined by bioimpedance: overhydration (OH)/extracellular water (ECW) > 15% (corresponding to 2.5L)
- normohydration defined as: ECW -6 to + 6% (corresponding to -1.1L to + 1L)

Correlation of volume status with patients' symptoms before haemodialysis based upon the symptom score developed by Kraemer et al⁸.

Symptoms of hypovolaemia:

- thirst directly after haemodialysis
- symptomatic hypotension, on change of position
- symptomatic hypotension
- nausea and vomiting
- muscle cramps
- limpness/ tiredness between dialysis sessions
- dizziness between dialysis sessions

Symptoms of hypervolaemia

- chronic coughing (new)
- dyspnea on recumbency
- dyspnea at rest; 1 pillow
- dyspnea at rest: 2 pillow
- dyspnea at rest: 3 pillows
- pretibial oedema
- paroxysmal nocturnal dyspnea (PND)

Correlates of volume status as measured by haemodialysis parameters including:

- total fluid removal (each haemodialysis session)
- IDWG
- proportion of haemodialysis sessions in which IDWG is $\leq 4\%$.
- pre-dialysis and post-dialysis weight
- pre-dialysis, intradialytic and post dialysis BP
- pulse rate
- requirement for nursing intervention such as stopping dialysis or administering fluid bolus
- adverse events including, but not limited, to muscle cramps, symptomatic hypotension, access-related complications, hypertension-related symptoms, congestive heart failure, pulmonary edema, requirement for additional unscheduled dialysis, or need for hospitalisation
- number and type(s) of BP medications
- home BP measured once/day during the interdialytic period

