5.1.2 Assessment of efficacy

The primary and secondary endpoint data will be listed and tabulated or displayed graphically.

The primary endpoint will be assessed by comparison of the fluid status variables observed via the Sixty device with those observed via bioimpedance and haemodialysis machine data and with symptoms.

The acceptability and utility of the Sixty device will be assessed by analysis of the responses to a patient questionnaire.

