6.3.2 Haemodialysis visits during study observation period

The patient will attend for haemodialysis as required for an observation period of approximately three weeks.

The patient will be asked to wear the Sixty device throughout the study observation period (approximately three weeks), except when bathing, swimming, showering or any other activity which would expose the device to large amounts of water.

At each clinic visit, before the patient starts haemodialysis the research team will remove the SD card from the patient's Sixty device and download the data collected in the previous 2-3 days. The SD card will be re-inserted into the Sixty device and the patient will put on the Sixty device at least five minutes before starting haemodialysis. The patient will wear the Sixty device during the haemodialysis procedure and the Sixty device will be recharged during haemodialysis. (The Sixty device will continue to collect data while recharging.) The patient will continue to wear the Sixty device until the next planned haemodialysis session.

The measurements related to haemodialysis and described in section 6.3.1 (usual care haemodialysis parameters and symptoms) will be recorded at each haemodialysis visit during the study observation period.

The patient will be asked to confirm that they have measured BP at home once/day during the study observation period.

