6.3.4 Week 3 visit (end of study observation period)

Before the patient starts haemodialysis the research team will remove the SD card from the patient's Sixty device and download the data collected in the previous 2-3 days. The Sixty device will be recharged and after recharging,

the patient will wear the Sixty device for at least five minutes before starting haemodialysis and during the haemodialysis procedure.

The measurements related to haemodialysis and described in section 6.3.1 (usual care haemodialysis parameters and symptoms) will be recorded at this visit.

In addition, fluid status will be assessed by bioimpedance immediately before and immediately after the start and end of haemodialysis.

The patient will wear the Sixty device during haemodialysis until at least five minutes after the end of the haemodialysis procedure. At this time, the research team will remove the SD card from the patient's Sixty device and download the data collected during this haemodialysis session.

The patient will return the Sixty device and the home BP monitor to the research team.

The patient will complete a questionnaire to give their opinion on the acceptability of the Sixty device be assessed and recorded.

The study procedures are concluded at this visit.

7. Statistical methods and determination of sample size

This a pilot-scale study to determine the validity and reproducibility of the data captured by the Sixty device in haemodialysis patients.

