7.3.1 Primary analyses

The objective of this pilot-scale study is to assess how the Sixty hydration monitoring device functions when used in a range of haemodialysis patients of varying age, gender, body habitus and volume status.

The primary endpoint will be assessed by comparison of the endpoint variables observed via the Sixty device with those observed via bioimpedance and haemodialysis machine data and symptoms.

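### Reproducibility is part of the primary objective, but the primary endpoint and its analysis define only comparisons with other measures, so the plan as written reports no reproducibility estimate

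*Protocol*

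**What the plan says.** Reproducibility is given as a purpose in four places in the protocol. Section 2.2 says: "The primary objective is to determine the validity and reproducibility of the data captured by the Sixty device". Section 3.2 adds: "The trial design will allow assessment of the validity and reproducibility of data collected by the Sixty device". Section 7 opens with: "This a pilot-scale study to determine the validity and reproducibility of the data captured by the Sixty device". Section 2.1 also pairs validity with reproducibility, there relative to reference measurements of fluid volume.

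The endpoint and analysis sections are narrower:

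- Section 5.1.1.1: "The primary endpoint will be to evaluate the accuracy of the Sixty device data in assessing volume in haemodialysis patients". The variables listed are comparison with bioimpedance, correlation with symptoms, and dialysis correlates of volume.
- Section 5.1.2: "The primary endpoint will be assessed by comparison of the fluid status variables observed via the Sixty device", set against bioimpedance, machine data and symptoms.
- Section 7.3.1: "comparison of the endpoint variables observed via the Sixty device with those observed via bioimpedance and haemodialysis machine data and symptoms".
- The statistical methods entry of the Protocol Summary plans a within-patient comparison, but between methods.
- Section 5.1.1.2 lists a general description of the device data, the proportion of sessions reaching normohydration, and acceptability.

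On handling of the device, Section 6.3.2 has staff download the SD card before dialysis and re-insert it, after which "the patient will put on the Sixty device at least five minutes before starting haemodialysis".

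**The concern.** Agreement with a reference method and reproducibility are different properties. A device can match bioimpedance on average and still give scattered readings, or give very stable readings that are consistently wrong. Readings from different sessions do not separate the two, because fluid status changes between sessions and that change is mixed with device error.

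Section 2.2 gives the underlying goal as judging whether the data can support algorithms for managing fluid between sessions, and that depends on how noisy a single reading is. Without a repeatability estimate, poor agreement with bioimpedance cannot be split into random device error and systematic disagreement. A pilot of a prototype should be able to tell the developer which of these it is.

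**Working it through.** **1. Text check.** There is no stated figure to reproduce: Section 7.6 calls n = 20 arbitrary, Section 7.2 states no hypotheses, and no alpha, power, SD or margin is given. The check is therefore whether each part of the objective has an endpoint and an analysis.

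| Place in protocol | Validity | Reproducibility |
|---|---|---|
| 2.1, 2.2, 3.2, opening of 7 (purpose) | named | named |
| 5.1.1.1 (primary endpoint) | defined | absent |
| 5.1.2 and 7.3.1 (assessment, analysis) | defined | absent |
| Protocol Summary, statistical methods | between methods | absent |
| 5.1.1.2 (secondary) | general description | no measure named |

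**2. Repeat data the schedule could supply.** Inputs: three sessions a week on average for about three weeks (6.1), 20 patients (7.6), and re-wear before each dialysis after the download (6.3.2). The baseline session has no earlier wear and gives no pair. Whether baseline counts among the nine sessions is not stated, so I assume 8 to 9 post-baseline sessions:

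- 20 × 8 = 160 pairs; 20 × 9 = 180 pairs, if none are missing.
- Leaving out week 3 removes one per patient: 20 × 7 = 140 to 20 × 8 = 160 pairs.

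**3. Precision of the within-patient SD.** From m pairs with differences d, the SD is s = √(Σd² / 2m), on m degrees of freedom if there is no systematic shift on re-wearing. The 95% limits, as multiples of s, are √(m / χ²₀.₉₇₅,ₘ) and √(m / χ²₀.₀₂₅,ₘ).

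| m | χ² upper, lower | 95% CI as multiple of s |
|---|---|---|
| 180 | 219.04, 144.74 | 0.91 to 1.12 |
| 160 | 196.92, 126.87 | 0.90 to 1.12 |
| 140 | 174.65, 109.14 | 0.90 to 1.13 |
| 20 (one pair per patient) | 34.17, 9.59 | 0.77 to 1.44 |

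The rows with several pairs per patient treat pairs as independent. If error size differs between patients, the true interval is wider, and the last row shows how wide it is with a single pair each. The repeatability coefficient is 1.96 × √2 × s = 2.77 s, so it carries the same relative uncertainty.

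**4. The Section 2.1 reading.** Bioimpedance is measured on four occasions (Section 6), before and after dialysis (flow chart, note B): 4 × 2 = 8 comparisons per patient and 20 × 8 = 160 in all. These could show whether agreement holds from visit to visit, but no analysis of that is defined either.

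**The case against.** The strongest reply is that Section 2.1 supplies the protocol's own meaning: reproducibility relative to reference measurements, that is, consistent agreement over repeated occasions. On that reading the four bioimpedance visits provide the data, the planned within-patient comparison is the vehicle, and only the summary statistic is missing, which an SAP may choose. This stands in part. It is a fair reading, and the fix should serve it. It does not close the gap, because the protocol itself fixes the primary endpoint as accuracy and says how it will be assessed. Choosing between an ICC and a repeatability coefficient is SAP detail; leaving part of the primary objective without any endpoint is not.

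A reader might go further and infer that the trial cannot report reproducibility, or that it produces no repeat pairs. The documents do not support that. The device records throughout wear, and what is missing is a defined analysis.

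A reader might also infer that re-wearing is a clean, cost-free test-retest. That is not supported either:

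- Removal just before the download is implied by the instruction to put the device on, not stated.
- The time off the wrist is not fixed. Intake, posture and sensor settling are not controlled.
- At week 3, Section 6.3.4 has the device recharged before it is worn again, so that gap may be longer.
- Removal and re-wear times are not recorded at present.

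Finally, re-wear pairs on one allocated device capture short-term repeatability and repositioning error only. About 10 devices serve 20 patients (7.6), so variation between devices stays largely mixed with differences between patients.

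**Conclusion.** The mismatch holds: reproducibility is named in the primary objective and appears in no endpoint or analysis. Followed as written, the plan reports no estimate of it, although the collected data could supply one. This should be corrected before enrolment, because the re-wear times must be logged as they happen. It does not undermine the validity comparisons, and in a descriptive pilot it is a matter of alignment and lost information.

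The count of 160 to 180 pairs is a best case. It assumes 8 to 9 post-baseline sessions, 20 patients with full wear and no missing readings; Section 8.5 allows a lower recruitment target. The interval of about 0.90 to 1.12 also assumes independent pairs. Even one usable pair per patient, at 0.77 to 1.44, would be informative for a pilot. What those pairs can support is a statement about short-term, same-device repeatability, not about reproducibility in every sense.

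**What to change.** Add a descriptive reproducibility endpoint to Section 5.1.1.1 and the matching analysis to Section 7.3.1:

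1. **Re-wear repeatability.** Report the within-patient SD and the repeatability coefficient (1.96 × √2 × SD), with a confidence interval that allows for clustering by patient. Use Sixty readings just before removal for the download and just after re-wearing, both before dialysis starts, in windows fixed in advance. State in 6.3.2 that the device stays on until the download, and have staff log removal and re-wear times.
2. **Week 3.** Report it separately or exclude it, because of the recharge before re-wear.
3. **Label.** Call the result short-term, same-device re-wear repeatability, and state that it does not measure between-device reproducibility.
4. **Consistency of agreement.** To cover the wording of Section 2.1, report how stable the Sixty-minus-bioimpedance difference is across the four bioimpedance visits (8 comparisons per patient), or the association if the units differ.

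The cost is a few sentences of protocol text, a small logging task at each session and one extra analysis. No visit or measurement is added.
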